## **CLINICAL BACKGROUND AND PROBLEM**

The efficacy and safety of endovascular thrombectomy (EVT) in patients with acute ischemic stroke (AIS) due to anterior circulation large-vessel occlusion (LVO) is well established in multiple randomized controlled trials (RCTs) in late treatment windows (6-16 hours)[2]. DEFUSE 3 (Endovascular Therapy Following Imaging Evaluation for Ischemic Stroke 3) and DAWN (DWI or CTP Assessment With Clinical Mismatch in the Triage of Wake-Up and Late Presenting Strokes Undergoing Neurointervention With Trevo), relied on CT perfusion(CTP) or magnetic resonance diffusion and/or perfusion, and utilized automated imaging analysis with Rapid Processing of Perfusion and Diffusion (RAPID; iSchemaView, Menlo Park, CA) software to determine eligibility. Some centers triage patients solely based on MRI imaging, because the use of emergency CT/MR perfusion is limited in many treating centers.

It has been found that the fluid attenuation inversion recovery vascular hyperintensity (FVH) sign is an indicator of large vessel occlusion or stenosis, inadequate collateral circulation leading to slow blood flow and early ischaemia. The presence of the FVH sign is not only fairly consistent with areas of low perfusion, but its sensitivity and specificity is similar to that of time-flight magnetic resonance angiography (TOF-MRA) for the diagnosis of large vessel occlusion.

At the same time, the appearance and distribution range of the FVH sign in patients with acute macrovascular occlusion were closely correlated with the hypoperfused areas and their corresponding mean passage times and cerebral blood flow revealed by CT perfusion imaging. It was thus hypothesized that FVH could be an important and convenient imaging manifestation reflecting the underperfusion of brain tissue in patients with cerebral infarction with macrovascular occlusion.

In this study, a randomised controlled approach was adopted to assess the risk and prognosis of endovascular treatment by using the "FVH-DWI mismatch" to determine the presence of an ischemic penumbra and collateral circulation in patients, with the aim of establishing a simple evaluation method based on the indirect evaluation of collateral circulation on MRI to screen patients who underwent thrombolysis at 6 to 24 hours overtime. These data will be used to help evaluate if there is a consistency in thrombectomy

treatment effect related to MRI and CTP/MR perfusion imaging profiles.but is more easily replicable.

## **STUDY INTRODUCTION**

### **1. The sponsor of this study**

The sponsor of this research project:Tianjin Huanhu Hospital

This study is a multicenter study,The role of our institution in this study: **team leader unit**

The department and principal investigator(PI) of the project: **Neurosurgery, PI: [name]**

### **2. Size of sample**

Total number of subjects planned to be included in this study: 214

### **3. Research Center**

The number of centers planned for this study: 5-10

### **4. Research Objectives**

**primary objective:**Evaluation of the effectiveness of screening patients with large vessel occlusion in acute ischemic stroke at 6-24h with the use of nuclear magnetic plain scan prior to emergency endovascular treatment

**Secondary objective:**Evaluation of the value of "**FVH-DWI Mismatch**" in the emergency endovascular treatment of patients with large vessel occlusion in 6-24h acute ischemic stroke

### **5. Study design**

#### **5.1 Study design**

The *MIEL* study is a multi-centre, prospective, randomized, open-label, blinded endpoint (PROBE) trial with a non-inferiority design. The study process was permitted by the ethics committee.

The study's emergency green channel team screened patients at 6-24 hours of onset for possible large vessel occlusion based on head CT scan and NIHSS score of  $\geq 6$  as the proposed cohort. Patients who met the entry criteria were then randomized 1:1 by the arriving stroke specialist into two groups 1 and 2 as follows, with the order of randomization being the responsibility of an independent investigator.

1.The MRI group performed DWI, FLAIRE, T1, T2 and MRA sequences.

2.The Control group underwent MRA or CTA, perfusion sequences, and F-stroke software (Brain Seal Smart Technology).

All patients were treated with standard Endovascular therapy and or optimal

drug therapy. The primary outcome was the overall distribution of modified Rankin scale scores at 90 days after surgery in the two groups of patients with modified intention-to-treat (**mITT**, defined as patients who had been optimally treated for acute macrovascular occlusion), as assessed by adjusted common odds ratios. Multiple secondary outcomes, including death, symptomatic intracranial hemorrhage, and ischemic regional reperfusion, were also assessed in the included study population.

## **5.2 Study population**

### **5.2.1 Inclusion and exclusion criteria**

#### **General inclusion criteria:**

1. Patients aged 18 years or older
2. Patients with acute anterior circulation ischemic stroke with an NIHSS score of  $\geq 6$  and RACE score  $\geq 5$  score at 6-24 hours of onset
3. No intracranial hemorrhage confirmed by cranial CT and CT ASPECTS score  $\geq 6$
4. Pre-onset Modified Rankin Scale (mRS) 0-2
5. Informed consent signed by all patients' legal representatives
6. Prognosis of survival 6 months or more.

#### **Exclusion criteria:**

1. Active hemorrhage or preexisting tendency to hemorrhage
2. CT shows hypointense areas exceeding 1/3 of the middle cerebral artery supply area, with significant midline structural displacement of cerebral edema
3. Rapid neurological improvement, NIHSS score less than 6, or evidence of spontaneous revascularization
4. Signs and symptoms typical of posterior circulation stroke, such as vertigo, nystagmus, choking, swallowing disorder, ataxia, and gaze to the affected side
5. A stroke attack with epilepsy that prevents an accurate NIHSS score from being obtained.
6. A platelet count of less than  $100 \times 10^9 /L$
7. Hereditary or acquired bleeding tendency, coagulation factor deficiency, recent anticoagulant medication (INR  $>3$  or PPT more than 3 times normal)
8. Presence of signs of cardiac, hepatic or renal failure
9. Baseline blood glucose  $<50\text{mg/dL}$  ( $2.78\text{mmol}$ ) or  $>400\text{mg/dL}$  ( $22.20\text{mmol}$ )
10. Uncontrolled hypertension (SBP  $>185\text{mmHg}$ ; DBP  $>110\text{mmHg}$ )
11. Expected survival less than 90 days.
12. Pregnancy.
13. Chronic obstructive pulmonary disease, inflammation of the lungs, pleural effusion, ARDS, irregular breathing and other pulmonary diseases requiring emergency treatment.
14. Patients with unstable vital signs (heart rate  $\leq 50\text{bpm}$  or  $\geq 120\text{bpm}$ , oxygen

saturation less than  $\leq 90\%$ .  $R \geq 30\text{bpm}$  or  $\leq 10\text{bpm}$ .

15. Patients who are unable to complete the 90-day follow-up

16. A history of severe allergy to contrast media

17. The presence of any other condition that is not suitable for endovascular treatment.

### **5.22 Subject Withdrawal from the Study**

Although subjects are discouraged from withdrawing from the study, subjects may withdraw from the study at any time and for any reason without consequence. No consequences will be incurred, and further treatment will not be affected.

Subjects may withdraw from the study for the following reasons:

(1) Subject withdraws informed consent to participate in the study and refuses further follow-up

(2) Any clinical adverse event, laboratory test abnormality, or concurrent disease that, in the opinion of the investigator, is not in the best interest of the patient

(3) Other circumstances that, in the opinion of the investigator, warrant withdrawal from the study

(4) Loss to follow-up

(5) Death of the subject

(6) The investigator terminates the study

### **5.3 Study methodology**

The study was designed as a randomized, double-blind, multicenter clinical trial.

#### **5.31 Study groups**

1. The MRI group performed DWI, FLAIRE, T1, T2, and MRA sequences.

2. The Control group performed perfusion sequences and processed them with F-Stroke stroke software (Brain Seal Smart Technology)

#### **5.32 Blind method**

Emergency department physicians were not aware of the experimental and grouping results.

The physician responsible for the assessment and the patient are aware of the grouping results; the attending physician is aware of the experimental and grouping results. Two neurointermediaries were assigned to the experiment. Two neurointerventionalists evaluate the procedure based on the readings provided by the respective group and decide whether to proceed. A third senior neurointerventional specialist decides.

The committee responsible for assessing primary and secondary outcomes and the imaging center specialists were not informed of the subgroup results. Outcome analysis was performed by an independent statistician, and results

were reported directly to the data and safety regulatory committee without the investigator being aware of the results at this time.

### 5.33 Study Implementation Process

Patient enrollment methods:

- A) Emergency greenway triage based on signs and symptoms and NCCT: In this study, a team of emergency department neurologists screened patients for possible large vessel occlusion at 6-24 hours of onset based on head CT scan and NIHSS score  $\geq 6$  and RACE score  $\geq 5$  as proposed subjects.
- B) Clearly diagnosed acute large vessel occlusion (ELVO)

Patients who have performed one of the MRI plain or perfusion examinations but do not meet the inclusion criteria for the DAWN or DEFUSE3 studies may be considered for inclusion. After enrollment, the appropriate imaging modality was selected according to the group as the basis for whether or not to perform interventional treatment.

Screening may be included in cases where either MRI or perfusion imaging is available at the time of the stroke specialist's evaluation of the patient, but the patient or authorized delegated family member is temporarily unable to decide whether to undergo the procedure, or under special irresistible conditions such as occupancy of the interventional suite.

Patients who met the entry criteria were then randomized 1:1 by the arriving stroke specialist into two groups 1 and 2 as follows, with the order of randomization being the responsibility of an independent investigator.

1. The MRI group performed DWI, FLAIRE, T1, T2 and MRA sequences.
2. The Control group underwent MRA or CTA, perfusion sequences, and F-stroke software (Brain Seal Smart Technology).

After randomization, the attending interventionalist decided the treatment based on the history and imaging data of the respective group. All patients were treated with the standard embolization procedure and or the optimal drug therapy. The primary outcome was the overall distribution of **MITT** patients' modified Rankin Scale scores at 90 days postoperatively in both groups, as assessed by the corrected co-ratio. Multiple secondary outcomes, including death, symptomatic intracranial hemorrhage, and

ischemic regional reperfusion, and safety outcomes were also assessed for the included study population.

#### **5.34 Statistical methods**

The primary efficacy analyses were performed by shift analysis, applying cumulative ordinal logistic regression to estimate the common OR and to evaluate the improvement in mRS scores in the **mITT** population. For secondary efficacy and safety analyses, statistical significance of differences between groups was assessed by Pearson  $\chi^2$  test or Fisher exact test for categorical variables, and by t test or Mann-Whitney test for continuous variables and safety endpoints for all patients. Descriptive analyses of adverse events were presented in the form of totals and events. Multivariate logistic or ordinal regression analyses were applied to determine independent estimators of good functional outcomes and were expressed as OR values and their 95% confidence intervals (95% CI). Two-sided values of  $P < 0.05$  were considered statistically significant. All statistical analyses were performed with IBM SPSS Statistics for Windows, version 19 (IBM Corp).

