### **5.37 Outcomes**

The primary outcome was the modified Rankin Scale score (mRS 90d) of a randomized group of modified intention-to-treat (mITT) patients (defined as patients with acute macrovascular occlusions treated optimally with endovascular or pharmacologic therapy) at 90 days (with an assessment time window of  $\pm 14$  days) and analyzed for noninferiority. If the primary analysis indicated possible superiority, superiority was tested as a secondary objective. Data were collected by structured interviews (telephone interviews) with patients using a standardized form by trained physicians who were unaware of the subgroup results. A standardized written report of each interview was presented to two members of the outcome committee, who confirmed the scores and reached agreement.

The secondary outcomes were as follows:

Proportion of patients in each group receiving interventions Good prognosis for patients receiving interventions

- 1) Patient death within 90 days.
- 2) Successful reperfusion after embolization, defined as an extended Thrombolysis in Cerebral Infarction (eTICI) score of 2b, 2c or 3 at the time of the first intracranial angiogram.
- 3) Percentage of patients revascularized 24 to 72 hours after surgery (as determined by CTA).
- 4) NIHSS scores at 24 hours and 5 to 7 days postoperatively (or at discharge).
- 5) Final infarct volume (calculated by CBV or DWI) at 24 hours and 5 to 7 days postoperatively (or at discharge).
- 6) Comparison of modified Rankin scores at 90 days (0 or 1 vs. 2-6; 0-2 vs. 3-6; 0-3 vs. 4-6; 0-4 vs. 5 or 6; and 0-5 vs 6).
- 7) Quality of life assessment at 90 days: European Five Dimensions and Five Levels Scale (EQ-5D-5L) scores (range, -0.39 [worst] to 1.00 [best]); Barthel

Index scores at 90 days (range, 0 [severe disability] to 100 [no disability]).

Safety outcomes: included all hemorrhage and symptomatic intracranial hemorrhage (Judged by the Heidelberg Classification of Hemorrhage); intraoperative arterial puncture site pseudoaneurysm and inguinal hematoma, cerebral infarction in an additional vascular area at 5 to 7 days, and death within 90 days. The timing of clinical evaluation included at baseline, 24 hours after randomization, 5 to 7 days, or at discharge, whichever occurred first, and 90 days (with an assessment time window of  $\pm 14$  days).

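### The protocol declares a non-inferiority trial, but its statistical methods section gives no margin or confidence-bound rule, only a two-sided P < 0.05 threshold

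*Protocol*

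**What the plan says.** Section 5.1 of the protocol calls the study a "randomized, open-label, blinded endpoint (PROBE) trial with a non-inferiority design". It gives the primary outcome as the 90-day mRS distribution in the mITT population, "as assessed by adjusted common odds ratios". Section 5.37 says that the 90-day mRS is "analyzed for noninferiority. If the primary analysis indicated possible superiority, superiority was tested as a secondary objective".

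Section 5.34 describes the primary analysis as a shift analysis, "applying cumulative ordinal logistic regression to estimate the common OR and to evaluate the improvement in mRS scores". It then lists the secondary and safety tests. After these come multivariable models to "determine independent estimators of good functional outcomes and were expressed as OR values and their 95% confidence intervals", followed by the general convention "Two-sided values of $P < 0.05$ were considered statistically significant".

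Section 2 states "Total number of subjects planned to be included in this study: 214", with no margin, power, assumed mRS distribution or allowance for losses. No margin for the common odds ratio appears in the protocol text supplied.

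**The concern.** A non-inferiority trial needs a margin and a rule that sets a confidence limit against it. Section 5.34 has neither. Its wording and its threshold are those of a superiority test against an odds ratio of 1. That is the question section 5.37 ranks second.

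Two things are at stake. First, if the strategies perform equally, which is the situation a non-inferiority design is built for, the written threshold gives almost no route to the declared conclusion. Second, with no margin fixed, a reader could take a non-significant P as success, or a margin could be chosen once results are known. Neither would be credible. Nor does P < 0.05 settle the matter, because it can equally mean that MRI selection is worse.

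**Working it through.** **1. What each result would allow under the written threshold.** Take the common odds ratio (OR) as MRI versus control, with OR > 1 favouring MRI.
- 95% CI entirely above 1 (P < 0.05): superiority is shown, and non-inferiority follows for any margin below 1.
- 95% CI includes 1 (P >= 0.05): no conclusion. With no margin, nothing shows whether the lower limit is acceptable.
- 95% CI entirely below 1 (P < 0.05): significant, but MRI is worse.

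Only the first result validly supports non-inferiority.

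**2. Inputs for the size of the problem.** From the protocol: N = 214, 1:1 allocation, two-sided 0.05. The 214 cannot be reproduced, because none of the inputs behind it is given. Assumed: an unadjusted common OR, proportional odds, all 214 in the mITT set, and control mRS 0 to 6 shares of 0.10, 0.17, 0.18, 0.16, 0.15, 0.08, 0.16 (mRS 0-2 = 45%). As a sensitivity case, 171 in the mITT set, about 80% of 214 (0.80 x 214 = 171.2). The 80% is only an illustration.

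**3. Standard error (Whitehead).** V = N(1 - sum p^3)/12 and SE(log OR) = 1/sqrt(V), where p is the mean share in each category.
- At OR 1, sum p^3 = 0.0238, so V = 214 x 0.9762/12 = 17.41 and SE = 0.240.
- With 171: V = 171 x 0.9762/12 = 13.91 and SE = 0.268.
- Three other assumed distributions, with mRS 0-2 of 30%, 35% and 55%, give SE 0.240 to 0.241 at N = 214. The assumed shares hardly matter.

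**4. Probability of significant superiority.** This is Phi(log OR/SE - 1.96).
- OR 1: Phi(-1.96) = 2.5%.
- OR 1.2: Phi(0.182/0.240 - 1.96) = Phi(-1.20) = 11.5%.

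**5. Probability of P >= 0.05 when MRI is worse.** This is about Phi(1.96 - |log OR|/SE); the other tail is negligible. Under proportional odds, control odds for mRS 0-2 are 0.45/0.55 = 0.818. OR 0.6 gives 0.491/1.491 = 33%, and OR 0.7 gives 0.573/1.573 = 36%.

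| True OR | mRS 0-2, MRI vs control | N = 214 | N = 171 |
|---|---|---|---|
| 0.6 | 33% vs 45% | 43% | 52% |
| 0.7 | 36% vs 45% | 68% | 74% |

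**6. Power under a proper rule, true OR 1.** The rule is that the lower 95% limit lies above margin M; power = Phi(-log M/SE - 1.96).
- M = 0.60: Phi(0.511/0.240 - 1.96) = 57% (48% with 171).
- M = 0.70: Phi(0.357/0.240 - 1.96) = 32% (26% with 171).

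**7. Orientation only.** The margin that 214 patients support at one-sided 2.5% and 80% power is exp(-(1.960 + 0.842) x 0.240) = 0.51. It is 0.46 at 90% power, 0.55 at one-sided 5% and 80% power, and 0.47 with 171 patients at one-sided 2.5% and 80% power. For 80% power, N = 12((1.960 + 0.842)/log M)^2/(1 - sum p^3), about 370 for M = 0.60 and about 760 for M = 0.70.

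**8. Check.** A simulation of 40,000 trials with the proportional-odds score test (N = 214) gave P >= 0.05 in 43.3% at OR 0.6 and 68.4% at OR 0.7. It gave significant superiority in 2.6% at OR 1 and 11.5% at OR 1.2. The lower limit exceeded 0.60 in 56.7% and 0.70 in 32.1% at OR 1.

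**The case against.** The best defence reads the sections together: 5.37 supplies the hypothesis and 5.34 the estimator. A common odds ratio from ordinal regression is a sound estimator for non-inferiority, and nothing here faults the model. The P < 0.05 sentence is a general convention near the end of 5.34, not expressly tied to the primary analysis. In a translated text, the word improvement may simply describe the direction of a shift. The 95% CI sentence covers multivariable ordinal models, and the adjusted common odds ratio of 5.1 would come from such a model. The SAP was not seen, nor were the flow chart and the appendix the protocol cites. The protocol nowhere says that a non-significant P shows non-inferiority, or that a margin will be chosen late.

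Some of this stands. The 2.5% and 11.5% figures apply if the P < 0.05 convention governs the primary analysis. The P >= 0.05 figures measure a misreading that the text leaves open but does not prescribe. The two-sided 95% limit is one convention among several.

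The defence still does not supply a rule. Under the joint reading, an estimated odds ratio has nothing to be compared with except 1, and a confidence interval without a margin decides nothing. The margin defines the primary hypothesis and underlies the sample size, so it is more than detail left to an SAP. Even if an SAP states one, 5.34 would still have to be brought into line with 5.1 and 5.37.

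**Conclusion.** The concern holds, and this must be fixed. The decision threshold in 5.34 does not answer the primary question set in 5.1 and 5.37, and a core design element, the margin, is absent from the protocol text supplied. That conclusion needs no numerical assumption.

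The size of the consequence rests on the unadjusted proportional-odds approximation and the assumed mRS shares. It is stable over the four distributions tried but approximate, because 5.1 specifies an adjusted odds ratio. On that basis, a trial of two equal strategies would validly reach its declared conclusion about 1 time in 40. Treating non-significance as success would pass a strategy that lowers mRS 0-2 from 45% to 36% about two times in three. The supported margins and larger sample sizes are for orientation and are not part of the finding itself.

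**What to change.** Amend 5.34, with matching text in 5.37 and section 2:

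1. Define the direction of the adjusted common odds ratio (MRI versus control, above 1 favouring MRI). Declare non-inferiority if the lower limit of its two-sided 95% CI lies above a stated margin.
2. Justify the margin on clinical grounds, independently of the sample size, and fix it before any unblinded data are seen. Do not work it back from 214.
3. Keep superiority as the second step, as 5.37 intends. Test it only once non-inferiority is met, by whether the same lower limit exceeds 1.
4. State that P >= 0.05 against an odds ratio of 1 does not show non-inferiority.
5. Beside the 214 in section 2, state the power it gives for that margin, allowing for patients who leave the mITT set.

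The rule itself costs only a text amendment. The possible further cost lies in the margin. If the justified margin is tighter than 214 patients can support, the sponsor must either report the low power openly or enlarge the trial. Under the assumptions above, 80% power at a true odds ratio of 1 needs about 370 patients for a margin of 0.60 and about 760 for 0.70.

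### Binary safety endpoints are assessed only by tests of difference, with no interval planned, in a non-inferiority trial of about 107 per arm; for low-rate events such as symptomatic intracranial haemorrhage these tests say little

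*Protocol*

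**What the plan says.** The protocol describes a "blinded endpoint (PROBE) trial with a non-inferiority design" (section 5.1). Section 2 gives the size: "Total number of subjects planned to be included in this study: 214". Patients are "randomized 1:1 by the arriving stroke specialist into two groups" (section 5.1).

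Non-inferiority is attached to one endpoint. Section 5.37 says that the 90-day mRS is collected "and analyzed for noninferiority". The safety outcomes in the same section "included all hemorrhage and symptomatic intracranial hemorrhage", and also cover puncture-site complications, infarction in a new territory and death within 90 days.

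The safety method is in section 5.34: "For secondary efficacy and safety analyses, statistical significance of differences between groups was assessed by Pearson" chi-square or Fisher exact test for categorical variables. The sentence then gives the t test or Mann-Whitney test for continuous variables and, in the same clause, "safety endpoints for all patients". Two-sided P values below 0.05 "were considered statistically significant". Adverse events are to be described by counts. The only 95% confidence intervals that section 5.34 names belong to odds ratios from multivariable models of good functional outcome. No expected rate, acceptable excess or interval is given for any safety endpoint.

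**The concern.** The trial asks whether selecting patients by plain MRI is no worse than selecting them by perfusion imaging. A test of difference answers another question: whether the data contradict exact equality. If it is non-significant, the data may be compatible with no excess, or with a large one, and the P value does not tell these apart. Only an interval does.

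The number of patients follows from the trial as a whole and is not justified for safety. For an uncommon event, a non-significant P value is then the expected result over a wide range of true harm. At stake is the content of the safety report. A non-inferiority result on mRS could stand beside P values for symptomatic haemorrhage that carry almost no information, with nothing to show how large an excess remains possible.

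A smaller matter lies in the wording. The safety endpoints appear in the clause on tests for continuous data, although those listed in section 5.37 are mainly yes/no events.

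**Working it through.** **Inputs from the protocol.** Total 214 (section 2); allocation 1:1 (section 5.1); two-sided 0.05, Pearson or Fisher (section 5.34). Per arm: 214 / 2 = 107, a derived figure. The protocol states no power, effect size, margin or dropout with the 214, so there is no figure of its own to reproduce here.

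**Inputs assumed.** The protocol gives no event rates. Control rates from 3% to 20% are used to show the range.

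**Power to detect a doubling.** With control risk p and MRI risk 2p, power is the sum over all pairs (a, b) of Bin(a; 107, p) × Bin(b; 107, 2p), counting only the pairs for which the test gives P < 0.05. This is an exact enumeration, with the Pearson test uncorrected.

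| Control v MRI | Pearson | Fisher |
|---|---|---|
| 3% v 6% | 17% | 10% |
| 5% v 10% | 29% | 21% |
| 6% v 12% | 35% | 26% |
| 8% v 16% | 45% | 36% |
| 10% v 20% | 55% | 47% |
| 15% v 30% | 76% | 70% |
| 20% v 40% | 90% | 87% |

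Power for a doubling passes 50% at a control rate of about 9% (Pearson) or between 10.5% and 11% (Fisher). Below that, a doubling is missed more often than not; above it, it is usually found. For 80% power by the normal approximation, the trial would need 435 per arm at 5% v 10%, 199 at 10% v 20% and 82 at 20% v 40%. If only 90 per arm could be analysed (an assumption), power at 5% v 10% falls to 24% / 17%.

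**Death, a smaller relative rise.** At 18% v 25% (ratio 25 / 18 = 1.4) power is 24% / 19%. At 15% v 22% it is 26% / 21%, and at 20% v 27% it is 23% / 18%. These are not doublings and should not be pooled with the table. A doubling of death from 18% to 36% would be detected with 85% / 81%.

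**Width of the interval when the observed rates are equal.** Half-width = 1.96 × √(2p(1 − p) / 107).

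- p = 6%: 1.96 × √(2 × 0.06 × 0.94 / 107) = 0.064, or ±6.4 points.
- p = 18%: 1.96 × √(2 × 0.18 × 0.82 / 107) = 0.103, or ±10.3 points.

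**What the interval adds.** Suppose 12/107 (MRI) and 6/107 (control) have symptomatic haemorrhage.

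- Difference: 0.112 − 0.056 = 0.056, or +5.6 points.
- Pearson: pooled rate 18 / 214 = 0.084; standard error √(0.084 × 0.916 × 2 / 107) = 0.038; z = 0.056 / 0.038 = 1.48; P = 0.14. Fisher gives P = 0.22.
- Newcombe 95% interval: Wilson limits are 2.6% to 11.7% (control) and 6.5% to 18.6% (MRI). Lower limit 5.6 − √((11.2 − 6.5)² + (11.7 − 5.6)²) = −2.1 points; upper limit 5.6 + √((18.6 − 11.2)² + (5.6 − 2.6)²) = +13.6 points (computed from unrounded values).

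An observed doubling is thus reported as non-significant, while an excess of nearly 14 points is not excluded.

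**The case against.** The strongest objection is that the harm lies in a conclusion the protocol never draws. A reader might infer that a non-significant safety result will be taken as equal safety. No section says so: non-inferiority is tied to the mRS outcome, and no safety claim of that kind is made. This stands. The point must rest on what section 5.34 fixes as its method, and not on a misreading it might invite.

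A reader might also infer that a doubling of any haemorrhage would usually go undetected. The figures do not support that. All haemorrhage is a separate endpoint, and at control rates of 15% or more a doubling would usually be found. The point is limited to low-rate events.

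Third, estimates and interval methods are often left to the statistical analysis plan, which is not shown, and tests of difference for safety are common in non-inferiority trials. This lowers the weight of the point but does not remove it. Section 5.34 is not silent on safety: it chooses a method, and that method is poorly suited to the design. Common use does not make it informative at this size.

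Fourth, death is partly covered elsewhere. It enters the primary outcome as mRS 6 and is one of the listed mRS splits (0-5 v 6). Disabling haemorrhage also reaches the mRS through its effect on function. This stands for death, and only indirectly for haemorrhage.

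Last, it is tempting to say that the protocol assigns a test for continuous data to yes/no events. The same sentence already gives Pearson or Fisher to categorical variables, and the phrase on safety endpoints may be meant to name the population. It is an ambiguity, no more.

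**Conclusion.** The concern holds in limited form. Section 5.34 assesses binary safety endpoints by two-sided tests of difference and names no interval for them. With about 107 per arm, that method cannot show that safety is no worse. For control rates of 3% to 8%, it would detect a doubling with a power of only 17% to 45% (Pearson) or 10% to 36% (Fisher). It does not extend to doublings of events with control rates of 15% or more. For death, a rise from 18% to 25% would be detected with 24% / 19%, with the reservation that death also counts in the primary outcome.

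All the rates are assumptions, because the protocol gives none; that symptomatic intracranial haemorrhage falls in the low range is also an assumption. The per-arm number assumes that all 214 are randomised and analysed. The change is worth making because it improves the safety report at almost no cost; the protocol contains no false safety claim.

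**What to change.** In section 5.34:

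1. For each binary safety endpoint, report the number and proportion per arm and the risk difference (MRI minus control) with a 95% confidence interval by the Newcombe or Miettinen-Nurminen method. This can stand beside the P value or replace it.
2. State that P of 0.05 or more is not evidence of equal safety, and that statements about safety refer to the upper confidence limit of the excess risk.
3. Reword the test sentence so that binary safety endpoints fall under Pearson or Fisher, and t or Mann-Whitney applies to continuous variables only. Keep, as a separate statement, that safety is analysed in all patients. Simply deleting the phrase would lose the safety population.

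The cost is a few sentences, with no extra patients or data. The downside is that the safety statement becomes less favourable, because the excess that the data do not exclude is shown. The interval informs the reader but is not a decision rule, since no acceptable excess is set for safety.

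### Section 5.34 calls every secondary comparison with two-sided P<0.05 significant; over about 15 comparisons, five of them nested cuts of the primary mRS, the chance of a false significant result is substantial

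*Protocol*

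**What the plan says.** Protocol section 5.34 names one primary analysis, the shift in 90-day mRS estimated as a common odds ratio in the mITT population. It then turns to the rest: "For secondary efficacy and safety analyses, statistical significance of differences between groups was assessed by Pearson" chi-square or Fisher tests for categorical variables, and t or Mann-Whitney tests for continuous ones. A single threshold closes the section: "Two-sided values of $P < 0.05$ were considered statistically significant". Nothing limits that sentence to the primary analysis, and nothing in the protocol calls the secondaries exploratory.

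Section 5.37 gives the list to which the rule applies. It opens with an unnumbered line, "Proportion of patients in each group receiving interventions Good prognosis for patients receiving interventions", and continues with seven numbered items. Item 6 cuts the primary scale five ways: "Comparison of modified Rankin scores at 90 days (0 or 1 vs. 2-6; 0-2 vs. 3-6; 0-3 vs. 4-6", then 0-4 vs 5-6 and 0-5 vs 6. The same section sets an order for the primary outcome, non-inferiority first and then: "If the primary analysis indicated possible superiority, superiority was tested as a secondary objective".

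**The concern.** The two sections together form a decision rule: test each secondary difference, and call it significant if P<0.05. With about 15 comparisons, a report that follows the plan exactly can claim a significant benefit or harm of MRI selection on whichever one crosses the line.

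The mRS cuts matter most. They re-test the primary scale five times at full alpha. One cut can therefore be declared significant, in either direction, whatever the common odds ratio shows. That opens a second route to a superiority or harm statement beside the sequence in 5.37. In an open-label strategy trial planned for 214 patients, such a statement could be read as a main result.

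**Working it through.** **Counting the comparisons (section 5.37).**

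| Outcome | Comparisons |
|---|---|
| Proportion receiving intervention; good prognosis in those treated (unnumbered) | 2 |
| Death within 90 days (item 1) | 1 |
| Successful reperfusion, eTICI (item 2) | 1 |
| Revascularisation at 24-72 h (item 3) | 1 |
| NIHSS, two times (item 4) | 2 |
| Final infarct volume, two times (item 5) | 2 |
| mRS cuts (item 6) | 5 |
| EQ-5D-5L and Barthel Index (item 7) | 2 |
| **Total** | **16** |

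Death and mRS 0-5 vs 6 are almost the same comparison, so about 15 are distinct. Safety outcomes are left out of this count.

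**Stated level.** Two-sided 0.05 per test. The protocol states no family-wise rate, so there is no figure of its own to reproduce.

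**Expected number of false positives under equal strategies.** 15 × 0.05 = 0.75, whatever the correlation.

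**Independent tests.** The chance of at least one P<0.05 is 1 − 0.95^k:
- k = 15: 1 − 0.463 = 0.537
- k = 16: 0.560
- k = 13 (without the two unnumbered outcomes): 1 − 0.513 = 0.487

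**Correlated tests.** The outcomes are related: the mRS cuts are nested, and NIHSS, infarct volume, Barthel, EQ-5D-5L and death all follow the same disability. The protocol gives no correlations, so they are assumed and varied.

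(a) 15 equally correlated normal test statistics, by simulation:

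| Correlation | Chance of at least one P<0.05 |
|---|---|
| 0 | 54% |
| 0.3 | 46% |
| 0.5 | 36% |
| 0.7 | 26% |
| 0.8 | 20% |

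(b) Patient-level simulation with no treatment difference, 107 per arm (214 from section 2, 1:1 from section 5.1), and 2,000 trials per setting. One latent severity drives all outcomes except whether a patient is treated. The mRS distribution, the event rates and a 65% share treated with thrombectomy are assumptions.

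| Loading on latent severity | Chance of at least one P<0.05 among 15 |
|---|---|
| 0.3 | 44% |
| 0.5 | 40% |
| 0.7 | 34% |

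The Monte Carlo standard error is about √(0.4 × 0.6 / 2000) = 1.1 percentage points.

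**The five mRS cuts alone.** If independent: 1 − 0.95^5 = 22.6%. In the patient-level runs they give 15-17%. A larger simulation (40,000 null trials for each of four assumed mRS distributions, 107 per arm, Pearson tests) gives 16.7-17.2%. Each single cut rejects in 4.6-5.2% of trials, so the per-test level is sound.

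**The case against.** The strongest reply is that multiplicity among secondaries is commonly settled in a statistical analysis plan, which is not shown, and that 5.34 only states a conventional per-test level. Much of this stands. The absence of a hierarchy or an alpha split is not an error in the protocol, and 5.34 claims no family-wise control. What remains is that 5.34 is not silent: it says significance of secondary differences is assessed and attaches an unqualified threshold. An analysis plan that labelled these outcomes exploratory would have to depart from that text.

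Other parts of the reply also hold:
- **The count is partly interpretive.** The opening line of 5.37 runs two outcomes together, and good prognosis is not defined there. The proportion treated compares two different selection rules, so a shared null is doubtful for it. Dropping both leaves 13 comparisons, and the conclusion hardly changes.
- **Superiority on the primary is already confined by 5.37.** Testing it after non-inferiority on the same endpoint costs no extra alpha.
- **Death within 90 days and mRS 6 are not exactly the same event**, because mRS is assessed with a ±14-day window. Counting them once is an approximation for the calculation, not a reason to merge them in the report.

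A reader might infer more than the documents support. One inference is that a false significant result is more likely than not. That needs near-independence, which is implausible for these outcomes. Another is that the stated 5% is wrong. It is a per-test level and it holds per test.

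**Conclusion.** The point holds as one about how secondary efficacy results may be claimed. Followed as written, the rule gives a chance of at least one false significant secondary result of about 34-46% under assumed low to moderate correlation. High correlation (0.7-0.8) lowers this to about 20-26%. Independence gives about 54%, which is the top of the range for positively related outcomes such as these. The five mRS cuts alone contribute about 15-17%.

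These figures rest on the count of about 15, on no true difference in any outcome, and on assumed correlations, event rates and mRS distributions. The conclusion is not sensitive to them: even the lowest figure is well above the 5% of a single test. The primary non-inferiority conclusion, the sample size and the conduct of the trial are untouched.

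**What to change.** Add to section 5.34, in words such as:

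> Secondary efficacy outcomes are exploratory. They are reported as effect estimates with 95% confidence intervals, without adjustment for multiplicity, and are not declared statistically significant. The five mRS dichotomies are presented together as a description of the common odds ratio and do not support a claim of superiority or harm outside the sequence in section 5.37. Safety outcomes are not subject to this restriction and are reported with estimates and unadjusted confidence intervals.

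Two cautions on wording:
- The change should not make two-sided P<0.05 the decision rule for non-inferiority. A test of difference does not establish non-inferiority, so the primary decision rule should be left out of this sentence.
- mRS 0-5 vs 6 and death within 90 days should stay as separate lines, since their time windows differ.

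The cost is a few sentences, with no extra patients, data or procedures. The real loss is that an isolated P<0.05 on a secondary efficacy outcome can no longer be reported as a significant finding.
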